4. ENDPOINTS

Primary Efficacy/Safety Endpoint(s):

This study has no primary efficacy or safety endpoints.

Primary Immunogenicity Endpoint(s)

Memory response, against the OAg of *S. sonnei* will be evaluated by measuring IgG Geometric mean concentrations (GMCs) 7 days after vaccination as determined by ELISA with O-antigen containing LPS as coating antigen.

Secondary safety endpoint(s):

The measures of safety will include:

- a. Numbers of subjects with deviations from normal values of hematological tests after vaccination.
- b. Numbers of subjects with solicited local and systemic reactions during 7 days following vaccination. Solicited local reactions include injection site erythema, injection site induration and injection site pain; solicited systemic reactions include headache, arthralgia, chills, fatigue, malaise, myalgia, and fever (as measured orally).
- c. Numbers of subjects with reported unsolicited adverse events (of any nature and severity) during 84 days following vaccination.

d. Number of subjects with reported SAEs throughout the study duration.

Secondary Immunogenicity Endpoint(s)

- a. IgG Geometric mean concentrations (GMCs) at 7, 14, 28 and 84 days after vaccination as determined by ELISA and applicable geometric mean ratios between post vaccination and baseline samples.
- b. Number and percentage of subjects with seroresponse for anti- LPS *S. sonnei* at 7, 14, 28 and 84 days after vaccination. Seroresponse is aimed to define a significant increase in post vaccination samples based on the biological performance of this specific serology assay and it is defined as follows:
 - If the baseline value is greater than 50 ELISA Units (EU) then an increase of at least 50% in the post-vaccination sample as compared to baseline [i.e. $((\text{Post-vac} - \text{baseline})/\text{baseline})100\% \geq 50\%$].
 - If the baseline value is less or equal to 50 EU then an increase of at least 25 EU in the post-vaccination sample as compared to baseline [i.e. $(\text{Post-vac} - \text{baseline}) \geq 25 \text{ EU}$].
- c. Number and percentage of subjects with titers post vaccination concentration ≥ 121 EU/ml for anti-LPS *S. sonnei* at 7, 14, 28 and 84 days after vaccination.

A post-vaccination concentration ≥ 121 anti-LPS serum IgG units in the GVGH ELISA with O-antigen containing LPS as coating antigen corresponds to a titer of 1:800 in the ELISA method used by Cohen et al. ([1989 J. Clin. Microbiol. 27:162](#)). This antibody level is the median antibody concentration of a set of 87 convalescent subjects previously infected by *S. sonnei*. The value of 121 anti-LPS serum IgG units in the GVGH ELISA was determined by calibration against the Cohen ELISA (i.e., the GVGH standard serum was tested in Cohen's lab using the Cohen's methodology).

The serologic assays on clinical samples will be performed at GSK, Clinical Laboratory Science (CLS), Marburg, Germany, or a delegated laboratory.

Exploratory Immunogenicity Endpoint(s):

Other assays, including serum secretory IgA, might be done to further characterize the immune response to the study vaccine. The analysis will be described in the statistical analysis plan.

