2.2 Secondary Objective(s)

Secondary Safety Objective(s)

- a. To evaluate the safety profile of one dose of GVGH *S. sonnei* 1790GAHB vaccine in subjects who previously received three vaccinations with 1790GAHB and in subjects receiving one dose 1790GAHB for the first time (either placebo recipients in H03_01TP or naïve subjects who were not part of H03_01TP study).
- b. To evaluate the safety profile of one dose of GVGH *S. sonnei* 1790GAHB vaccine in subjects receiving one dose 1790GAHB for the first time and having detectable antibodies at baseline of the extension trial. **Secondary Efficacy Objective(s)**

This study has no secondary efficacy objectives.

Secondary Immunogenicity Objective(s)

- a. To evaluate the immunogenicity profile 7, 14, 28 and 84 days after vaccination with one dose of GVGH *S. sonnei* 1790GAHB in subjects with undetectable antibody titers at baseline who previously received three vaccinations of 1790GAHB in H03_01TP and in placebo recipients with undetectable antibody titers at baseline in H03_01TP or naïve subjects who were not part of H03_01TP study.
- b. To evaluate the immunogenicity profile of one dose of GVGH *S. sonnei* 1790GAHB vaccine in subjects receiving one dose 1790GAHB for the first time and having detectable antibodies at baseline of the extension trial.
- c. To evaluate the persistence of anti-LPS *S. sonnei* serum IgG antibody titers approximately two to three years after the third vaccination with 1790GAHB.

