8.4.2.3.3 Statistical Methods

Analysis of continuous variables

The ELISA concentrations will be logarithmically transformed (base10) (to fulfil the normal distribution assumption). GMC will be calculated, with their associated two-sided 95% CIs, by exponentiating the corresponding log-transformed means and their 95% CI.

Additionally, within-subject GMRs will be computed for GMTs/GMCs at 7, 14, 28 and 84 days after vaccination versus baseline (day 1). The GMRs and 95% CIs will be constructed by exponentiating the mean within-subject differences in log-transformed titers and the corresponding 95% CIs. Analysis of binary variables

The number and percentages of subjects with seroresponse from baseline and with high antibody level after vaccination (i.e. post vaccination antibody level ≥ 121 IgG units in the GVGH ELISA), will be summarized. Two-sided 95% Clopper-Pearson CIs for the percentages will be computed.

Titers below the limit of detection will be set to half that limit for the purposes of analysis. Missing values of immunogenicity will be excluded from analyses (i.e. complete-case analysis) since they are considered missing completely at random, i.e. not informative and with no impact on inferences

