2. STUDY DESIGN

This is an open label, non-randomized, single center, Phase 1 clinical trial. The study includes a screening visit (performed at study Days -21 to -1), one clinical visit with vaccination (performed at study Day 1), 4 clinical visits (performed 7, 14, 28 and 84 days after vaccination), and 2 phone calls (performed 2 and 6 days after the vaccination).

Table 2-1 H03_01TP Study Design

| H03_01TP | H03_01E1TP | | | |
|---------------|---------------|-----------------------|--------------|---------------|
| | | | | |
| Vaccine group | No. subjects* | New enrolled subjects | No. subjects | Vaccine group |

| | | | |
|-------------------|----|----------------|------------------|
| 1790GAHB – 1 µg** | 5 | 5 | 1790GAHB – 25 µg |
| 1790GAHB – 5 µg | 4 | 4 | 1790GAHB – 25 µg |
| 1790GAHB – 25 µg | 2 | 2 | 1790GAHB – 25 µg |
| 1790GAHB – 50 µg | 4 | 4 | 1790GAHB – 25 µg |
| 1790GAHB – 100 µg | 5 | 5 | 1790GAHB – 25 µg |
| Placebo | 4 | 4 | 1790GAHB – 25 µg |
| Total H03_01TP | 24 | Naïve subjects | 26 |
| Grand total | | | 50 |

*only subjects with undetectable antibodies at baseline.

** µg of total protein

Up to 50 subjects will be enrolled into this trial. Up to 24 subjects are eligible from the parent H03_01TP trial. With respect to naïve subjects who were not part of H03_01TP study, considering that in the original H03_01TP population 50% of subjects did not have detectable antibodies at baseline, with 26 subjects, approximately 13 subjects should not have detectable antibodies. This number combined with that of placebo recipients in H03_01TP should be sufficient to allow a balanced contribution of previously unvaccinated and vaccinated subjects in the extension trial.

Blood Draw Procedure

A blood draw will be obtained for hematological and serological (HIV, hepatitis B and C) tests for subjects who were part of the parent trial (H03_01TP). For naïve subjects a blood draw will be obtained for the same hematological and serological tests mentioned above and in addition for HLA-B27 testing as part of the initial screening.

One additional blood draw for hematological tests will be obtained at 7 days (Visit 2) and 84 days (Visit 5) after vaccination.

Each subject will have blood drawn for immunological studies before and 7, 14, 28 and 84 days after vaccination. For the purpose of creating a standard reference serum for the serological assay, an additional blood sample will be collected at 28 days after vaccination (Visit 4).

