3. OBJECTIVES

Primary Objective(s):

To evaluate the memory response, as measured by anti-LPS *S. sonnei* serum IgG, 7 days after vaccination with a booster dose of GVGH *S. sonnei* 1790GAHB vaccine in individuals who had undetectable antibody titers at baseline in H03_01TP, approximately two to three years after the third vaccine dose, compared to administration of 1 single vaccine dose to placebo recipients with undetectable antibody titers at baseline in H03_01TP or naïve subjects who were not part of H03_01TP study.

Secondary Objective(s):

1) Safety:

- a. To evaluate the safety profile of one dose of GVGH *S. sonnei* 1790GAHB vaccine in subjects who previously received three vaccinations with 1790GAHB and in subjects receiving one dose 1790GAHB for the first time (either placebo recipients in H03_01TP or naïve subjects who were not part of H03_01TP study).

- b. To evaluate the safety profile of one dose of GVGH *S. sonnei* 1790GAHB vaccine in subjects receiving one dose 1790GAHB for the first time and having detectable antibodies at baseline of the extension trial.

2) Immunogenicity:

- a. To evaluate the immunogenicity profile 7, 14, 28 and 84 days after vaccination with one dose of GVGH *S. sonnei* 1790GAHB vaccine in subjects with undetectable antibody titers at baseline who previously received three vaccinations of GVGH *S. sonnei* 1790GAHB vaccine in H03_01TP and in placebo recipients with undetectable antibody titers at baseline in H03_01TP or naïve subjects with undetectable antibody titers at baseline who were not part of H03_01TP study.
- b. To evaluate the immunogenicity profile of one dose of GVGH *S. sonnei* 1790GAHB vaccine in naïve subjects receiving one dose 1790GAHB for the first time and having detectable antibodies at baseline of the extension trial.
- c. To evaluate the persistence of anti-LPS *S. sonnei* serum IgG antibody titers approximately two to three years after the third vaccination with 1790GAHB.

3) Exploratory:

Other immunological assays might be performed to further characterize the immune response to the study vaccine including serum secretory IgA.

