6.4. Immunogenicity

6.4.1. Analysis of immunogenicity planned in the protocol

The FAS will be the primary analysis set for the immunogenicity objective.

Within group assessment

For the immunogenicity profile in terms of anti-LPS *S. sonnei* serum IgG antibody titers, at each timepoint that a blood sample is available, the following parameters (with two-sided 95% Confidence Intervals (CIs)) will be estimated for each treatment group:

- Geometric mean concentration (GMC)
- Seroresponse rate for anti- LPS *S. sonnei* IgG
- Percentage of subjects with post vaccination concentration ≥ 121 EU/ml
- Geometric mean Ratio (GMR): Post vaccination GMC versus baseline (day 1)

In addition, the distribution of antibody titres for Shigella and Placebo+Naïve group for each visit where blood sample was collected will be displayed using reverse cumulative distribution curves.

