6.4.2. Additional considerations

The percentage of subjects with seroresponse by titer at baseline and with post vaccination antibody level ≥ 121 IgG units

Pearson CIs will be computed by vaccine group at each visit and associated two-sided 95% Clopper-

Unadjusted GMCs and associated two-sided 95% CIs will be computed for each group at each visit. For each vaccine group, unadjusted GMCs and their 95% CIs will be obtained by exponentiating (base 10) the least square means and the lower and upper limits of the 95% CIs of the log-transformed titers or concentrations (base 10).

Titers below the limit of detection will be set to half that limit for the purposes of analysis. Missing values of immunogenicity will be excluded from analyses (i.e. complete-case analysis) since they are considered missing completely at random, i.e. not informative and with no impact on inferences

The immunogenicity tables will show some or all of the following subgroups. See mock up tables.

Shigella group: subjects from parent study H03_01TP who previously received three vaccinations with 1790GAHB regardless of the total protein amount.

Placebo group: subjects from parent study H03_01TP who previously received vaccinations with Placebo.

Naïve group: naïve subjects enrolled in H03_01E1TP.

Pla+Naïve: subjects from parent study H03_01TP who previously received vaccinations with Placebo plus naïve subjects enrolled in H03_01E1TP

Subjects with detectable antibodies at baseline (i.e. with antibodies at baseline \geq Lower Limit of quantification, LLOQ)

Subjects without detectable antibodies at baseline (i.e. with antibodies at baseline $<$ LLOQ)

Note that in Shigella and Placebo groups the LLOQ was assessed at the baseline of the parent study H03_01TP, while in Naïve group the LLOQ will be assessed at baseline of extended study H03_01TP.

1MG_SHI, 5MG_SHI, 25MG_SHI, 50MG_SHI, 100_MG_SHI: subjects from parent study H03_01TP who previously received vaccinations with GVGH *Shigella sonnei* 1790GAHB vaccine containing 1 mcg, 5 mcg, 25 mcg, 50 mcg, 100 mcg of total protein amount respectively.

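### The primary objective compares booster with first-dose response at 7 days, but the visible plan defines no between-group estimate and does not label the comparator (all first-dose subjects, up to 30, or only the undetectable ones, about 17)

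*SAP*

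**What the plan says.** The primary objective (SAP 3, same wording in Protocol 2.1) sets the booster response at 7 days against a first dose: "compared to administration of 1 single vaccine dose to placebo recipients with undetectable antibody titers at baseline in H03_01TP or naïve subjects" from outside the parent study. The SAP's primary endpoint, memory response, "will be evaluated by measuring IgG Geometric mean concentrations (GMCs) 7 days after vaccination as determined by ELISA" (study Day 8). SAP 6.4.1, under a heading that announces within-group assessment, says "the following parameters (with two-sided 95% Confidence Intervals (CIs)) will be estimated for each treatment group": GMC, seroresponse rate, percentage at or above 121 EU/ml, and the GMR of post-vaccination to Day 1. SAP 6.4.2 adds unadjusted GMCs and Clopper-Pearson intervals by group. Protocol 8.4.2.3.3, the methods section for the primary objective, has the same per-group content. The only display naming both sides is a set of reverse cumulative curves for Shigella and Placebo+Naïve.

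On the comparator, the passages pull two ways:

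- **All first-dose subjects.** The primary objective puts no serostatus limit on naïve subjects, SAP 6.4.2 defines Pla+Naïve without one, and the curves use that pooled group.
- **Undetectable only.** The sample-size rationale in SAP 2 counts about 13 undetectable naïve subjects and says "This number combined with that of placebo recipients in H03_01TP should be sufficient to allow a balanced contribution" of vaccinated and unvaccinated subjects. SAP secondary immunogenicity objective 2a restricts its naïve arm to "naïve subjects with undetectable antibody titers at baseline who were not part of H03_01TP study".

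SAP 6.4.2 defines detectable and undetectable subgroups but leaves the choice of rows open: "The immunogenicity tables will show some or all of the following subgroups. See mock up tables". Annex 3 says only that standard mocks apply. SAP 9 records no change from plan.

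**The concern.** A descriptive trial needs no test, but a stated comparison still needs a named estimate. Following the visible text gives two GMCs, each with its own interval. A reader can divide them for a point ratio, but has no interval for that ratio, and the two group intervals do not supply one.

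With the comparator unlabelled, the answer to the primary question can also shift with whether detectable naïve subjects are counted.

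There is an interpretive point too. Shigella-group serostatus was set before three priming doses, and persistence of antibody is itself secondary objective 2c. Part of that group's Day-8 GMC may therefore be antibody already present on Day 1. The plan collects and summarises what is needed to separate the two (Day-1 GMCs and within-group GMRs) but does not contrast it between groups.

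**Working it through.** **1. The plan's counts (SAP Table 2-1).** Primed: 5 + 4 + 2 + 4 + 5 = 20. With 4 placebo recipients: 24. With 26 naïve subjects: 50. Expected undetectable naïve subjects: 26 × 0.5 = 13. All match the SAP. The comparator is therefore 4 + 13 = 17 or 4 + 26 = 30. The 13 is an expectation: under Binomial(26, 0.5) the central 95% range is 8 to 18, giving a comparator of 12 to 22.

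**2. Precision of a between-group GMC ratio.** The documents give no SD, so log10 SDs of 0.3, 0.5 and 0.7 are assumed. The interval is the ratio times or divided by

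10^( t(0.975, n1+n2−2) × SD × √(1/n1 + 1/n2) ).

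For 20 vs 17 at SD 0.5: t = 2.030, the root is 0.330, and 10^(2.030 × 0.5 × 0.330) = 10^0.335 = 2.16.

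| Groups | SD 0.3 | SD 0.5 | SD 0.7 |
|---|---|---|---|
| 20 vs 17 | 1.59 | 2.16 | 2.94 |
| 20 vs 30, same SD in both groups | 1.49 | 1.95 | 2.55 |

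The 20 assumes that every eligible primed subject returns. The documents say up to 24 parent-study subjects are eligible, and withdrawals are not replaced. If only 12 primed subjects came back (assumed), 12 vs 17 at SD 0.5 gives t = 2.052, root 0.377, factor 2.44. At SD 0.5 a comparator of 12 to 22 against 20 gives 2.36 to 2.05.

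**3. What the planned intervals would give instead.** The group factor is 10^( t(0.975, n−1) × SD/√n ). At SD 0.5 it is 1.714 for n = 20 and 1.807 for n = 17. Dividing opposite limits multiplies these: 1.714 × 1.807 = 3.10, against the correct 2.16. At SD 0.3 and 0.7 the products are 1.97 and 4.87, against 1.59 and 2.94.

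**4. Effect of the comparator choice.** Suppose the 13 detectable naïve subjects have d times the Day-8 antibody of the other 17 (assumed). The GMC of all 30 is then d^(13/30) times that of the 17, and the booster/first-dose ratio falls by the same factor: 1.35 (d = 2), 2.01 (d = 5), 2.71 (d = 10).

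Mixing serostatus also widens the interval. The SD in the 30 becomes √(SD² + (log10 d)² × (13/30) × (17/30)). At SD 0.5 this is 0.522, 0.608 and 0.704 for d = 2, 5 and 10, and the Welch 20 vs 30 factor is 1.98, 2.08 and 2.20. The larger group therefore gains little over the 2.16 for 20 vs 17.

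Setting the shift equal to the Welch factor gives the d at which the choice matters as much as sampling error: 2.8, 5.5 and 10.8 for SD 0.3, 0.5 and 0.7. At SD 0.5, for example, 5.48^(13/30) = 2.09, equal to the interval factor there.

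**5. Day 8 and Day 1.** On log10 in the same subjects, the between-group difference at Day 8 equals the difference at Day 1 plus the difference in mean within-subject change. So Day-8 GMC ratio = Day-1 GMC ratio × ratio of GMRs. The Day-8 ratio alone does not separate a memory response from antibody already present.

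**The case against.** The strongest reply is that the trial is open-label, non-randomised and descriptive, with no hypothesis, success criterion or power calculation, so no decision depends on this ratio. That justifies the absence of a test. It does not justify leaving the only primary comparison without an estimate.

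Second, the table list and any mock shells (SAP 10) are not visible and may already contain a ratio or name the comparator. That is possible. The point concerns the SAP text, and if the shells settle it, one sentence in the SAP suffices.

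Third, a reader might infer that the pooled group is a mistake and that the 17 undetectable subjects are the intended comparator. The documents do not support that. The primary objective, the Pla+Naïve definition and the curves all lean to the full group, and the SAP added the serostatus limit to objective 2a but not to the primary objective beside it. Choosing the 17 is an estimand decision for the sponsor.

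Fourth, a reader might see a conflict over which baseline sets serostatus, because Protocol 2.2 objective b refers to "subjects receiving one dose 1790GAHB for the first time and having detectable antibodies at baseline of the extension trial", which could take in placebo recipients, whereas SAP 6.4.2 uses their parent-study baseline. The SAP settles this for immunogenicity: its objective 2b is limited to naïve subjects, and 6.4.2 assigns the parent baseline to Shigella and Placebo and the extension baseline to Naïve.

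Fifth, the plan does not rest on Day-8 GMCs alone. Day-1 GMCs, per-group GMRs and baseline-relative seroresponse are all planned. What is missing is their contrast between groups.

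**Conclusion.** The point holds as a cheap improvement. The visible text defines no between-group ratio or interval for the primary comparison, and the comparator is unlabelled between up to 30 and about 17 subjects. Descriptive intervals would be wide but usable: a factor of 1.59 to 2.94 for 20 vs 17 over assumed log10 SDs of 0.3 to 0.7, and wider if fewer primed subjects return.

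It would be too strong to say that the comparator choice dominates the result. Allowing for mixed serostatus, the shift reaches the interval factor only from d = 2.8, 5.5 or 10.8, depending on the SD, and at d = 2 it stays below every interval factor calculated here. Ignoring the extra spread would put these thresholds at 2.5, 4.7 and 8.7, which overstates the effect. The SDs, the values of d and the return rate are all assumptions. Only the counts come from the documents.

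**What to change.** In SAP 4 and 6.4, descriptively and with no test:

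1. For the primary objective, add the Shigella / first-dose ratio of Day-8 GMCs with a t-based 95% CI on the log10 scale. Beside it, give the between-group ratio of within-subject Day-8/Day-1 GMRs with a 95% CI. Put both in one table with the planned Day-1 GMCs and read them together.
2. Report both ratios for all Pla+Naïve and for undetectable first-dose subjects, with the serostatus baseline as already set in SAP 6.4.2. The sponsor states before analysis which is the primary comparison. If it is the undetectable group, record that in SAP 9, since it is narrower than the literal objective.
3. If the table list already holds such a ratio or comparator, say so in the SAP text.

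The cost is some SAP wording and a few table rows from data already collected, with no new samples or assays. The two ratios may disagree and need joint reading. Because the groups are not randomised, both remain descriptive.
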